4. STUDY DESIGN

4.1. Study Overview

This is a prospective, open label, single arm, single dose study in subjects with solid tumor brain metastases previously treated with radiation therapy, designed to establish the diagnostic performance of ¹⁸F-fluciclovine PET (read with standard MRI for anatomical reference) in detecting recurrent brain metastases where MRI is equivocal.

Subjects with a history of brain metastases previously treated with primary, adjuvant or repeat (salvage) radiation therapy, with a recent SoC brain MRI found to be equivocal for recurrent brain metastasis, and who meet all inclusion criteria and none of the exclusion criteria, will be consented and enrolled. The study population will be balanced to represent different primary tumor types of any origin, with a minimum of approximately 15% of the cohort each with lung cancer, breast cancer and melanoma. The number of subjects with lung cancer will be capped at approximately 50% of enrolled subjects.

Investigator will prepare a diagnostic management plan prior to the ¹⁸F-fluciclovine PET scan and will update the plan following the scan. All eligible subjects will receive an ¹⁸F-fluciclovine PET scan (Visit 2 PET) within 42 days of SoC MRI. Subjects will then undergo a repeat study-specific brain MRI scan (Visit 2 On-Study MRI) to be used for anatomical reference, ideally on the same day, otherwise ≤ 3 days after Visit 2 PET and completed before any pre-planned neurosurgical intervention when applicable. A Safety Follow-up (Visit 3) 1 to 3 days after IMP injection/PET (Visit 2 PET) will be made for AE evaluation by telephone call or in person (if same day as other scheduled SoC appointments). AEs occurring from the time of ¹⁸F-fluciclovine administration until 1 day post-¹⁸F-fluciclovine administration will be recorded. The Safety Follow-up must be completed before the pre-planned SoC biopsy/neurosurgical intervention, if applicable. Subjects who experience an SAE or an AE that persists at Visit 3, will be followed until resolution or stabilization of these events. All ongoing follow-up and any further treatment will be in accordance with SoC.

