As MRI is not specific for tumor recurrence in this setting, current clinical practice is mainly focused on close clinical follow-up to determine the presence of recurrence. Alternatively, biopsy or direct neurosurgical intervention of the abnormality may be performed. This study will utilize all available diagnostic and follow-up clinical data to establish the underlying diagnosis. The planned diagnostic method will be recorded at Screening and assessed for any changes following ¹⁸F-fluciclovine PET scan.

If biopsy/neurosurgical intervention has been pre-planned per SoC, the Visit 2 PET will be organized to take place a minimum of 1 day and maximum of 21 days before pre-planned SoC biopsy or neurosurgical intervention.

On-site investigators will prospectively annotate and measure the 'reference lesion' on a post-radiation treatment MRI scan and on the pre-study SoC MRI scan to confirm eligibility.

The 'reference lesion' is defined as the lesion which is:

- a. Equivocal for recurrent metastasis on SoC MRI (according to inclusion criterion #7, see [Section 6.2](#)).
- b. Intended for SoC biopsy/neurosurgical intervention procedure (if planned). If >1 lesion is intended for biopsy/intervention, the largest of these lesions will be the reference lesion.

- c. Where clinical follow-up is planned, the largest of all equivocal lesions (if >1 is present) will be the reference lesion.

If >1 equivocal lesion is under evaluation as SoC, the on-site investigator will also annotate 'other equivocal lesions' on the pre-study SoC MRI scan, defined as follows:

- a. Equivocal for recurrent metastasis on SoC MRI (according to the same radiological criteria for a reference lesion per inclusion criterion #7, see [Section 6.2](#)).
- b. Where SoC biopsy/neurosurgical intervention procedure is planned, these are the other equivocal lesions pre-planned for biopsy/intervention.
- c. Where SoC clinical follow-up is planned, these are the other equivocal lesions pre-planned for SoC clinical follow-up.

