10.4. Visit 3 – Safety Follow-up (+1 to 3 days after IMP Injection/PET)

1. Clinical safety review by telephone call (or in person if same day as scheduled SoC biopsy, Visit 2 MRI, or other planned visit) to assess concomitant medications and AEs.
2. Record any changes in concomitant medications since Screening (Visit 1).
3. Record any AEs which have occurred during the safety reporting period (from the time of ¹⁸F-fluciclovine administration until 1 day post ¹⁸F-fluciclovine administration). For scheduling purposes, the subject may be contacted up to 3 days after IMP injection, but the assessment is to be limited to the first day after IMP injection only.

10.5. Visit 4 – SoC Biopsy/Neurosurgical Intervention (if applicable, pre-planned 1 to 21 days after IMP Injection/PET)

Where this visit is applicable, SoC biopsy/neurosurgical intervention should also take place after both the Visit 2 on-study MRI brain scan and Visit 3 Safety Follow-up.

1. Document neurosurgical procedure:
 - a. Record sites of reference lesion and other equivocal lesions which underwent SoC biopsy, and where applicable, ‘additional PET lesion(s)’, if performed.
 - b. Record sites of reference lesion and other equivocal lesions which underwent resection, and where applicable, ‘additional PET lesion(s)’, if performed.*
- c. If applicable, record neuronavigation system used for neurosurgical procedure.

* *Undertaking biopsy/resection of additional PET lesion(s) identified on the ¹⁸F-fluciclovine PET scan is at the discretion of the on-site investigators. The lesions should be judged suggestive of brain metastasis, warranting confirmation according to SoC practice. The subject will receive post-procedural management per institutional SoC.*

- d. Where biopsy was performed, upload image/screenshot of neuronavigation system depicting stereotactic coordinates of biopsy. Where resection was performed, upload image/screenshot of neuronavigation system depicting the surgical resection plan/approach (if neuronavigation was not used for resection, a representative screenshot of the post-procedure MRI demonstrating the resection cavity is suitable).
- e. Upload neurosurgical procedural report.
- f. Record any clinical factors associated with the neurosurgical intervention which impacted the type of procedure performed.

2. Label specimens with lesion ID as referenced by the imaging core laboratory study imaging platform on the previously annotated scans.

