12. ADVERSE EVENT REPORTING AND DOCUMENTATION

12.1. Adverse Events

An AE is any untoward medical occurrence in a clinical investigation subject administered a pharmaceutical product and that does not necessarily have a causal relationship with the treatment. An AE is therefore any unfavorable and unintended sign (including an abnormal laboratory finding), symptom or disease temporally associated with the administration of an investigational product, whether or not related to that investigational product. An unexpected AE is one of a type not identified in nature, severity, or frequency in the current Investigator's Brochure or is of greater severity or frequency than expected based on the information in the Investigator's Brochure.

The investigator will probe, via discussion with the subject, for the occurrence of AEs during each subject visit within the AE collection period. The collection period for all AEs will begin after initiation of ¹⁸F-fluciclovine injection and end 1 day post ¹⁸F-fluciclovine administration (i.e., Day 2). Any unresolved AE at Visit 3 Safety Follow-up beyond Day 2 will be followed until resolution or stabilization. The investigator will record the information in the site's source documents. Adverse events will be recorded in the subject electronic Case Report form (eCRF). Adverse events will be described by duration (start and stop dates and times), severity, outcome, treatment and relation to study drug.

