13.3. Lost to Follow-up

A subject will be considered lost-to-follow-up if there are no follow-up data at Visit 5 (183 days \pm 14 days) and the subject is unable to be contacted by the study site staff. Death will not be considered lost to follow-up.

The following actions must be taken if a subject fails to complete a required study visit:

- The site will attempt to contact the subject and reschedule the missed visit (if within acceptable visit windows), and ascertain if the subject wishes to and/or should continue in the study.
- Where a pre-scheduled Visit 4/Day 3-22 SoC biopsy/neurosurgical intervention is planned, the site will attempt to contact the subject and reschedule the missed visit prior to the SoC biopsy/neurosurgical intervention, and ascertain if the subject wishes to and/or should continue in the study.

- Before a subject is deemed lost to follow-up, the investigator or designee will make every effort to regain contact with the subject (where possible, 3 telephone calls and, if necessary, a certified letter to the subject's last known mailing address or local equivalent methods). These contact attempts should be documented in the subject's medical record or study file.
- Should the subject continue to be unreachable, he or she will be considered to have withdrawn from the study with a primary reason of lost to follow-up. A subject will be considered unreachable when:
 - Has received IMP and is beyond 183 days post-IMP administration.
 - Has not received IMP and is beyond 42 days of pre-study SoC MRI.

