15.6.6. Safety

Treatment-emergent adverse events (TEAEs) are defined as those AEs with onset after the dose of IMP, or existing events that worsened after the dose of IMP during the study, up to 1 day following IMP administration. Verbatim terms of the AEs will be coded to preferred terms (PTs) and system organ classes using the latest version of Medical Dictionary for Regulatory Activities (MedDRA), for data summary purposes. Severity of AEs will be graded using the NCI-CTCAE v5.0. The frequency of TEAEs will be summarized overall, by system organ classes and PT, and by severity. IMP-related AEs and SAEs will also be summarized.

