There will be no adjustments for multiple comparisons in the efficacy analysis for this study.

7.4.5.5 *Examination of Subgroups*

Subgroup analysis will be performed as described in section 7.4.4.3.

7.5 **Safety Evaluation**

Safety analysis will be carried out for the Safety analysis set, to include all subjects who have been dosed with IMP. Subjects who do not complete the study, for whatever reason, will have all available data up until the time of termination included in the analysis.

7.5.1 *Extent of Exposure*

Each subject will receive a single dose of ¹⁸F-fluciclovine by injection, 185 MBq (5 mCi) \pm 20%, delivered as an intravenous bolus by site staff. IMP administration data will be summarized, and details of administration will also be listed.

7.5.2 *Adverse Events*

Treatment-emergent adverse events are defined as those AEs with onset after the dose of IMP, or existing events that worsened after the dose of IMP during the study, up to 1 day following IMP administration. Events reported with a partial onset date (e.g., month and year are reported but the day is missing) will be considered to be treatment-emergent if it

cannot be confirmed that the event onset was prior to the dose of IMP based on the available date entries.

Adverse event verbatim terms will be coded to preferred terms and system organ classes using the latest version of MedDRA, version 23.0. Severity of AEs will be graded using the National Cancer Institute common terminology criteria for adverse events (NCI-CTCAE) v5.0.

Summaries that are displayed by system organ class (SOC) and preferred term (PT) will be ordered by descending incidence of SOC and PT within each SOC, and then alphabetically for SOC, and PT within SOC. Summaries of the following types will be presented:

- Overall summary of subject incidence of TEAEs by severity, relationship, and action taken, subject incidence of treatment-emergent serious adverse events (TESAEs) by relationship;
- Subject incidence of TEAEs by MedDRA system organ class and preferred term;
- Subject incidence of TEAEs by NCI-CTCAE grade, MedDRA system organ class, and preferred term;
- Subject incidence of TEAEs related to IMP by MedDRA system organ class, and preferred term;
- Subject incidence of TESAEs by MedDRA system organ class and preferred term;
- Subject incidence of TESAEs related to IMP by MedDRA system organ class and preferred term;

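### Visit 3, the only scheduled adverse-event contact after Day 1, may take place on Day 2 before the AE collection period has ended, so an early call leaves part of that period unasked

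*Protocol*

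**What the plan says.** **AE collection period.** Protocol 12.1 starts collection at injection and has it "end 1 day post ¹⁸F-fluciclovine administration (i.e., Day 2"; 12.4.1 sets the same limits for SAEs. Protocol 15.6.6 bounds treatment-emergent AEs (TEAEs) at "up to 1 day following IMP administration", and SAP 7.5.2 includes "existing events that worsened after the dose of IMP during the study, up to 1 day following IMP administration". Neither document says whether one day means 24 hours from injection or the end of calendar Day 2.

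**Contacts.** Visit 2 monitors and records AEs after injection and takes vital signs after the scan (10.2). The next scheduled AE contact is "Visit 3 – Safety Follow-up (+1 to 3 days after IMP Injection/PET", shown in Table 1 as Day 2 to 4. Section 10.4 adds that "the subject may be contacted up to 3 days after IMP injection, but the assessment is to be limited to the first day after" injection. Section 12.1 also has the investigator probe for AEs at every visit that falls inside the collection period.

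**Biopsy or surgery (Visit 4).** Section 4.1 says: "The Safety Follow-up must be completed before the pre-planned SoC biopsy/neurosurgical intervention, if applicable". Section 10.4 allows an in-person Visit 3 on the day of the biopsy. On the earliest day, 4.1 states that "the Visit 2 PET will be organized to take place a minimum of 1 day and maximum of 21 days before pre-planned" the procedure, whereas 13.3 reads "Where a pre-scheduled Visit 4/Day 3-22 SoC biopsy/neurosurgical intervention is planned".

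**The concern.** The first permitted day for Visit 3 is also the last day of the period it asks about. A site that injects in the afternoon and telephones next morning is inside the visit window, yet the rest of the period has not happened when the question is asked, and no later AE contact is scheduled. Observation time for TEAEs (secondary endpoint 6) would then differ between subjects according to the hour of the call.

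The two versions of the earliest Visit 4 day bear on this. If a procedure takes place on Day 2, Visit 3 has to precede it and may therefore close while the period is still open. Section 12.1 would cover the remaining hours by probing at that visit, but the task list for Visit 4 in 10.5 contains no AE step.

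**Working it through.** **Day arithmetic.** SAP 7.1.2 defines study day on or after dosing as event date minus dosing date plus one.

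- End of AE collection: 1 + 1 = Day 2, which reproduces the figure in 12.1.
- Visit 3 at 1 to 3 days: Day 2 to Day 4, which matches Table 1.
- Visit 4 at 1 to 21 days: Day 2 to Day 22, which matches the Visit 4 column headings.
- The version in 13.3, Day 3 to 22, converts back to 2 to 21 days after injection and does not match the one-day minimum in 4.1.

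**Where the earliest Visit 4 day appears.** Day 2: Protocol 4.1, the 10.5 heading, and the Visit 4 column headings in Protocol Table 1 and SAP 6.2. Day 3: Protocol 13.3, and the Visit 2 timing cell of the schedule in both documents.

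**Hours left unasked.** The documents give no clock times, so those below are assumptions. For injection at hour *i* on Day 1 and contact at hour *c* on Day 2, elapsed time is *t* = (24 − *i*) + *c*. Hours unasked are max(0, 24 − *t*) on the 24-hour reading, and 24 − *c* on the end-of-Day-2 reading.

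| Injection | Contact, Day 2 | Elapsed (h) | Unasked, 24 h reading | Unasked, end of Day 2 |
|---|---|---|---|---|
| 08:00 | 08:00 | 24 | 0 | 16 |
| 12:00 | 09:00 | 21 | 3 | 15 |
| 14:00 | 09:00 | 19 | 5 | 15 |
| 16:00 | 08:00 | 16 | 8 | 16 |
| 16:00 | 17:00 | 25 | 0 | 7 |

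Contact on Day 3 or Day 4 leaves 0 hours on either reading.

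**Bound on missed reactions.** Protocol 1.1 reports adverse reactions to the product in 17 of 1203 subjects: 17/1203 = 1.41%, and 1.41% × 150 enrolled = 2.12 expected. Take the extreme case that all 150 are injected at 14:00 and called at 09:00, and assume that onset is spread evenly over the period. The expected number with onset in the unasked hours is 2.12 × 5/24 = 0.44 on the 24-hour reading. On the end-of-Day-2 reading the period is 10 + 24 = 34 hours, which gives 2.12 × 15/34 = 0.94. Both are below one.

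**The case against.** The plan has safeguards, and most of the case against stands.

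- A reader might infer that Visit 3 is the only safety contact after dosing. It is not: Visit 2 monitors AEs after injection and takes vital signs after the scan.
- A reader might infer that late events are never asked about. That fails for every Day 3 or Day 4 call, and section 10.4 expressly lets those cover the first day. Any other visit inside the period must be probed under 12.1. SAEs suspected to be related remain reportable afterwards under 12.4.1.
- Section 10.4 tells sites to record AEs for the whole period, and its heading could be read as requiring at least 24 hours to have passed. On that reading together with a 24-hour period there is no gap. But Table 1 expresses the visit in calendar days, the SAP counts days by date, and no text makes elapsed time a condition of the call. This reply therefore narrows the gap without closing it.
- A reader might infer that surgical events will distort the safety tables and that the SAP needs parallel tables with and without them. The documents do not support that. TEAEs are counted whatever their cause. Protocol 12.3 classes events reasonably explained by concurrent treatment as not related. SAP 7.5.2 tabulates related TEAEs and related serious TEAEs separately and lists causality and study day of onset by subject. Overlap would also need PET, on-study MRI, Visit 3 and procedure all on Days 1 and 2, and no count of such subjects is given. Nor can surgical events be set against the 1.4% figure, which counts reactions attributed to the product.
- The Day 3 wording in 13.3 sits in a bullet on missed visits, not in a scheduling rule. That makes it a small inconsistency, but one repeated in the schedules of both documents.

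**Conclusion.** The point holds in a limited form. Visit 3 is the only scheduled AE contact after Day 1, it may fall on the last day of the collection period, and nothing requires that period to have ended. An early Day 2 call therefore leaves hours unasked: 0 to 8 on the 24-hour reading and 7 to 16 on the end-of-Day-2 reading, for the clock times assumed above.

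The consequence is possible incompleteness of a descriptive secondary safety endpoint. How many subjects would be called early is unknown, and the expected number of missed product reactions stays below one even in the extreme case computed, which rests on assumed clock times and even onset. The primary NPA and PPA analysis is unaffected. This is a cheap improvement, not a threat to the trial's conclusions.

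The conflict between Day 2 and Day 3 for Visit 4 is plain on the page and must be reconciled. Which day is right is for the clinical team.

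**What to change.** 1. In Protocol 10.4 and Table 1, for subjects with no procedure inside the AE collection period, have the Visit 3 AE question asked only once that period has elapsed. State in 12.1 whether the period is 24 hours or runs to the end of Day 2. The existing Day 2 to 4 window already accommodates this.
2. For subjects with a procedure inside the period, leave the order of Visit 3 and procedure as it is. Cover the remaining hours with the probing that 12.1 already requires at each visit, and add that step to the list in 10.5.
3. Reconcile the earliest Visit 4 day across Protocol 4.1, 10.5, 13.3 and Table 1, and SAP 6.2.

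The cost is a few lines of wording. The downside of the first change is that some calls move later, by up to a day. The second change imposes no timing on any procedure, and if the clinical team's reconciliation leaves no procedures inside the period, the added step is simply unused. No new SAP tables are needed.

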10.6. Visit 5 – Month 6 Follow-up (183 days ± 14 days)

All subjects will be followed for 6 months (183 days ± 14 days) following ¹⁸F-fluciclovine PET in order to collect diagnostic information (brain imaging scans, histopathological reports) and treatment regimens which will be provided to the Central Truth Panel ([Section 11.8](#)). Treatment regimens will pertain to treatments and therapies for the brain lesion(s) and primary tumor. These will include and are not limited to systemic treatments such as chemotherapy, immunotherapy and corticosteroids; and localized therapies such as radiotherapy, LITT and craniotomy.

The date and nature of the diagnosis (presence or absence of metastasis) of the reference, other equivocal and additional PET (if applicable) lesions reached by site will be collected. An assessment of neurological deterioration will be recorded. The subject mortality status will also be recorded, with collection of date and cause of death (if applicable).

Determination of a subject's mortality status must be verifiable from the medical record, including confirmation of death where applicable or, where alive, a documented clinical interaction (e.g. imaging scan, blood test, consult) taking place on or beyond Day 169. If the site is unable to verify mortality status from the medical record, additional steps will be undertaken, including a review of vital records or a documented phone call to the patient or the patient's family.

Therefore, this Visit comprises predominantly of investigator review of the subject medical record and will take place in the physical absence of the subject. Subjects whose reference or other equivocal lesion(s) continue to be considered at the site level to be equivocal for brain metastasis at Month 6 (Visit 5) will have a final research MRI unless an SoC MRI was performed within the prior 3 weeks.

10.7. Early Withdrawal

Early withdrawal is defined as discontinuing from study within 168 days of Visit 2. Death is not considered as early withdrawal.

- Record any AEs or changes to concomitant medication occurring during safety reporting period.
- Record reason for early withdrawal.
- Record clinical follow-up data to date of early withdrawal as detailed in Visit 5 evaluations (see [Section 10.6](#)).

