13. DISCONTINUATION AND REPLACEMENT OF SUBJECTS

13.1. Discontinuation/Withdrawal from the Study

Subjects are free to withdraw from participation in the study at any time, for any reason, specified or unspecified, and without prejudice.

An investigator may discontinue or withdraw a subject for the following reasons:

- Significant protocol violation or non-compliance.
- If any clinical AE, laboratory abnormality, or other medical condition or situation occurs such that continued participation in the study would not be in the best interests of the subject (investigator decision).
- Protocol violation requiring discontinuation of study treatment.
- If the subject meets the exclusion criteria (either newly developed or not previously recognized) that precludes further study participation.
- Lost to follow-up.
- Sponsor request for early termination of study.
- Subject requests to be withdrawn from the study.
- Positive pregnancy test (females).

The reason for subject discontinuation or withdrawal from the study, if known, will be recorded in the subject's source documents and in the eCRF.

Refer to [Section 10.7](#) for early withdrawal procedures.

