13.2. Replacement of Subjects

Subjects who sign the informed consent form (ICF) and do not receive the study scan may be replaced. Subjects who sign the ICF and receive the study scan, but the scan is not considered evaluable (refer to [Section 11](#) of the Imaging Protocol), may be replaced. Subjects who sign the ICF, and receive the study scan, and subsequently withdraw early (as defined in [Section 10.7](#)), or are withdrawn or discontinued from the study, may be replaced.

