7.2 Analysis Sets

The Full Analysis Set (FAS) will include all enrolled subjects dosed with IMP with an evaluable Visit 2 on-study PET scan. The FAS will be used for primary and secondary non-safety endpoints (including diagnostic performance and inter-reader and intra-reader assessment for the PET scans).

The Safety Analysis Set (SAF) will include all subjects dosed with IMP (with or without the associated PET scan). The SAF will be used for all safety analyses.

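### Follow-up data stop at the withdrawal date even when the investigator or sponsor ends participation after dosing, so obtainable reference-standard records are lost and the subject can be scored as a PET error

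*Protocol*

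**What the plan says.** Protocol 10.7 sets the scope: "Early withdrawal is defined as discontinuing from study within 168 days of Visit 2. Death is not considered as early withdrawal". For all such cases it then instructs sites: "Record clinical follow-up data to date of early withdrawal as detailed in Visit 5 evaluations". It does not distinguish who made the decision.

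Protocol 13.1 opens its list with "An investigator may discontinue or withdraw a subject for the following reasons", and the first reason is "Significant protocol violation or non-compliance". Section 14 adds that the sponsor decides whether a protocol violation leads to withdrawal. Neither section confines this to the time before injection.

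Protocol 4.1, 10.6 and 11.8.2 describe the intended data window as six months after the PET scan, or until death. None names withdrawal as an end point. Of Month 6 itself, Protocol 10.6 says that "this Visit comprises predominantly of investigator review of the subject medical record and will take place in the physical absence of the subject". An MRI is added only if a reference or other equivocal lesion is still equivocal at the site and there is no standard-of-care MRI from the preceding three weeks.

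On who is analysed, SAP 7.2 says: "The Full Analysis Set (FAS) will include all enrolled subjects dosed with IMP with an evaluable Visit 2 on-study PET scan". Protocol 13.2 says that subjects who are scanned and then withdraw early "or are withdrawn or discontinued from the study, may be replaced", but no rule takes the replaced subject out of the analysis set.

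SAP 7.4.5.1 covers a reference lesion whose panel result is missing or indeterminate. Recorded neurological deterioration makes it positive. Confirmed absence of deterioration on or after Day 141 makes it negative. Anything still unresolved is given, in the main analysis, the opposite of that reader's PET call.

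**The concern.** After the single injection, the 30-minute scan, the on-study MRI and the safety call, most of what the trial still needs from a subject lies in the standard-of-care record. When an investigator or sponsor withdraws a dosed subject, for example over an eligibility violation found late, that record goes on accruing. Protocol 10.7 nevertheless tells the site to stop abstracting it at the withdrawal date.

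The cut-off removes two things. The truth panel loses later imaging, histopathology and treatment data. The SAP's fallback rules lose their input as well: someone withdrawn before Day 141 cannot be confirmed free of deterioration on or after Day 141 if nothing is collected after withdrawal.

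Worst-case imputation suits data that cannot be obtained. Here the protocol itself stops the collection of data that could be obtained, and the SAP then counts the gap against the scan.

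**Working it through.** **Reading the rules in sequence for one subject.** Take a dosed subject with an evaluable PET whom the investigator or sponsor withdraws before Day 141.

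1. Protocol 10.7: data are recorded to the withdrawal date only.
2. SAP 7.2: dosed with an evaluable scan, so in the Full Analysis Set.
3. Protocol 13.2: may be replaced; no rule removes the subject from that set.
4. SAP 7.4.5.1: if the panel cannot decide on the truncated data and no deterioration was recorded, the result stays indeterminate.
5. Main analysis: a positive read becomes a false positive and a negative read becomes a false negative, separately for each of the three readers.

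**Reproducing the plan's power figure.** Inputs from SAP 7.6: N = 130, prevalence 0.5 (65 per class), goals of 50%, assumed rates of 70%, one-sided 0.025, exact binomial.

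- Smallest r with P(X ≥ r | 65, 0.5) ≤ 0.025 is r = 41, with exact alpha 0.0232.
- The Clopper-Pearson lower limit is 0.502 at 41/65 and 0.486 at 40/65, so the interval rule gives the same cut-off.
- P(X ≥ 41 | 65, 0.7) = 0.910. The stated 90% reproduces for each endpoint.
- For both endpoints together at a fixed 65/65 split: 0.910² = 0.828. If the split varies as Bin(130, 0.5), the joint chance is 0.79. That gap from 90% is a separate matter; 0.79 is the baseline here.

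**Effect of m unresolved subjects (m is assumed; the documents give no count).** One reader.

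- The chance of a positive read is 0.5 × 0.7 + 0.5 × 0.3 = 0.5. Of the m subjects, A ~ Bin(m, 0.5) become false positives and m − A become false negatives.
- With D resolved subjects, K ~ Bin(D, 0.5) are truly positive.
- Denominators: K + (m − A) for PPA and (D − K) + A for NPA.
- Correct calls: Bin(K, 0.7) and Bin(D − K, 0.7).
- Success requires both counts to reach the exact 0.025 cut-off for their own denominators.

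Scenario (a), set fixed at 130: D = 130 − m. Expected PPA and NPA are about 0.7 × (130 − m)/130.

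Scenario (b), replaced but retained: D = 130 and the set is 130 + m. Expected PPA and NPA are about 0.7 × 130/(130 + m).

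| m | (a) expected rate | (a) both goals met | (b) expected rate | (b) both goals met |
|---|---|---|---|---|
| 0 | 0.700 | 0.79 | 0.700 | 0.79 |
| 2 | 0.689 | 0.73 | 0.689 | 0.74 |
| 4 | 0.678 | 0.65 | 0.679 | 0.67 |

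Replacement recovers only a small part of the loss. For a single endpoint in scenario (a), with a fixed split, power goes from 0.910 to 0.878 (m = 2) and 0.839 (m = 4).

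**The case against.** The strongest reply is that few subjects will be affected. The reasons in 13.1 are permissive. The only prohibited medication is barred only until Visit 3 is complete. After that visit a non-surgical subject has no scheduled procedure before a possible Month 6 MRI, so there is little left to violate. Many withdrawn subjects would also be resolved in other ways: biopsy or surgery falls on Days 2 to 22, the panel may decide on data from before withdrawal, and the deterioration rules settle others. This stands. It limits the size of the problem but does not remove the mismatch between 10.7 and the six-month window elsewhere.

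Nor is Month 6 purely a chart review: the MRI for a still-equivocal lesion needs the subject, and continued abstraction cannot replace it.

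A reader might go further in several ways that the documents do not support.

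- **Loss to follow-up.** Section 13.3 treats a dosed subject as unreachable when he or she "Has received IMP and is beyond 183 days post-IMP administration", while the Visit 5 window runs to Day 197 (183 + 14). This does not feed the problem: a loss declared after Day 183 lies outside the 168-day definition, so the 10.7 cut-off does not apply.
- **Pregnancy as a post-dose route.** Tests are scheduled only at Screening and before injection, and 12.4.3 directs withdrawal for pregnancy arising between Screening and Visit 2.
- **Selective withdrawal.** Sites do see the PET scan, but every remaining indeterminate counts against the reader in the main analysis, so removing a subject by this route gains nothing there.
- **A margin of 4.5 subjects.** At 65 per class, 45.5 correct calls are expected and 41 are needed. The difference is in correct calls within one class. Each unresolved subject in a set of 130 costs about 0.7 × 0.5 = 0.35 expected correct calls per class, so about 4.5/0.35 ≈ 13 subjects would bring the expectation down to 41.
- **The 150-to-130 allowance.** It gives no bound on m, because replacement under 13.2 also covers unscanned subjects and non-evaluable scans, who never enter the analysis set.

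**Conclusion.** The concern holds in a limited form. Section 10.7 stops data at withdrawal whoever initiates it, at odds with the six-months-or-death window in 4.1, 10.6 and 11.8.2. A dosed subject withdrawn by the investigator or sponsor stays in the primary analysis. That subject is scored as an error for each reader only if three conditions all hold: the panel result is missing or indeterminate, no deterioration is recorded, and absence of deterioration is not confirmed on or after Day 141. It would be wrong to infer that every withdrawn subject becomes an error.

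The direction is conservative: PPA and NPA are biased down and power is lost, with no route to false success in the main analysis. Two to four such subjects would cost about 5 to 14 percentage points of the chance that one reader meets both goals. This assumes true rates of 70%, prevalence 0.5 and an even chance of a positive read among unresolved subjects. The counts of two and four are illustrative, and the true number is probably small. The change is worth making because the loss is avoidable and cheap to prevent.

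**What to change.** In Protocol 10.7 and 13.1, state that after IMP administration a withdrawal decided by the investigator or sponsor ends study procedures only. Month 6 record abstraction (imaging, histopathology, therapies, site diagnosis, neurological deterioration, mortality) continues through Day 183 ± 14 unless the subject withdraws permission to use records. These data go to the truth panel, except the site diagnosis, which 11.8.2 withholds from it. In the eCRF, record stopping procedures and withdrawing permission for records as separate items.

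The cost is protocol wording, one eCRF item and some extra chart abstraction. The consent form is not among the documents reviewed, so its wording must be checked to confirm that it permits continued use of records.
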